5.4.2.6. Management of Neutropenia

Nonclinical and clinical experience indicates that venetoclax may cause neutropenia. Subjects with a history of neutropenia who have received multiple prior therapies and/or have significant bone marrow involvement may be at a particularly high risk.

CTCAE Grade 3 or 4 neutropenia has been reported in patients treated with venetoclax. Complete blood counts should be monitored throughout the treatment period. Dose interruptions or dose reductions are recommended for subjects with severe neutropenia. Supportive measures including antimicrobials for any signs of infection and prophylactic use of growth factors (eg, G-CSF) should be considered.

5.4.2.7. Management of Hematologic Toxicities Other Than Neutropenia or Lymphopenia

Venetoclax treatment should be withheld for any CTCAE Grade 4 hematologic toxicity. Once the toxicity has resolved to Grade 1 or baseline level (recovery), venetoclax may be re-started at the same dose. If the toxicity recurs, the dose reduction guidelines in [Table 5](#) should be followed when resuming study treatment following resolution. Additional dose reductions may occur at the discretion of the physician.

5.4.2.8. Management of Non-Hematologic Toxicity

Venetoclax treatment should be withheld for any clinically relevant CTCAE Grade ≥ 3 non-hematologic toxicity. Once the toxicity has resolved to Grade 1 or baseline level (recovery), venetoclax may be re-started at the same dose. If the toxicity recurs, the dose reduction guidelines in [Table 5](#) should be followed when resuming study treatment following resolution. Additional dose reductions may occur at the discretion of the physician.

5.4.2.9. Management of Decrease in Spermatogenesis

Venetoclax may cause a decrease in spermatogenesis. Male subjects considering preservation of fertility should bank sperm before initiating treatment with venetoclax.

5.4.2.10. Embryo-Fetal Toxicity

Based on its mechanism of action and findings in animals, venetoclax may cause embryo-fetal harm when administered to a pregnant woman. In an embryo-fetal study conducted in mice, administration of venetoclax to pregnant animals at exposures equivalent to that observed in patients at the recommended dose of 400 mg daily resulted in post-implantation loss and decreased fetal weight. There are no adequate and well-controlled studies in pregnant woman using venetoclax. Advise females of reproductive potential to avoid pregnancy during treatment.

If venetoclax is used during pregnancy or if the subject becomes pregnant while taking venetoclax, the subject should be apprised of the potential hazard to the fetus.

5.4.2.11. Immunization

The safety and efficacy of immunization with live or attenuated viral vaccines during or following venetoclax therapy have not been studied. Immunization with live virus vaccines is not recommended during treatment and thereafter until B-cell recovery.

5.5. Criteria for Permanent Discontinuation of Study Drug

Investigators are encouraged to keep a subject who is experiencing clinical benefit in the study unless significant toxicity puts the subject at risk or routine noncompliance puts the study outcomes at risk. If a subject discontinues one study drug for reasons other than disease progression, the other study drug should be continued per protocol. Refer to Study Design details in [Section 3.1.1](#) and [Section 3.1.2](#). For a complete list of criteria for permanent discontinuation of study treatment, refer to [Section 9.2](#).

An End-of-Treatment Visit ([Section 8.7](#)) is required for all subjects except for those subjects who have withdrawn full consent.

6. CONCOMITANT MEDICATIONS/PROCEDURES

Concomitant therapies must be recorded from the time of ICF signing until 30 days after the last dose of study drug.

6.1. Permitted Concomitant Medications

Supportive medications in accordance with standard practice (such as for emesis, diarrhea, etc.) are permitted and patient should receive full supportive care during study participation (including fluids and electrolyte replacement, and antibiotics when appropriate). Use of neutrophil growth factors (filgrastim and pegfilgrastim) or red blood cell growth factors (erythropoietin) is permitted per institutional policy and in accordance with the ASCO guidelines ([Smith 2006](#)) except as outlined in [Section 6.2](#) below. Transfusions may be given in accordance with institutional policy.

After consultation with the Medical Monitor the following may be considered; localized, hormonal or bone sparing treatment for non-B-cell malignancies, and localized radiotherapy for medical conditions other than the underlying B-cell malignancies.

Short courses (<14 days) of steroid treatment for non-cancer related medical reasons (eg, joint inflammation, asthma exacerbation, rash, antiemetic use, and infusion reactions) at doses that do not exceed 100 mg per day of prednisone or equivalent are permitted.

Treatment for autoimmune cytopenias are permitted for <14 days at doses that do not exceed 100 mg per day of prednisone or equivalent.

6.2. Medications to Be Used with Caution

A sample list of cautionary medications with ibrutinib and venetoclax is provided in [Appendix G](#). Refer to [Table 7](#) below for management of potential ibrutinib and venetoclax interactions with CYP3A inhibitors.

6.2.1. Drugs That May Alter Ibrutinib and/or Venetoclax Plasma Concentrations

6.2.1.1. Concomitant Use with Ibrutinib

Ibrutinib is metabolized primarily by CYP3A4. Avoid co-administration with strong CYP3A or moderate CYP3A inhibitors and consider alternative agents with less CYP3A inhibition. Avoid grapefruit and Seville oranges during ibrutinib/placebo treatment, as these contain moderate inhibitors of CYP3A (see [Section 5.4.1.2](#)).

- If a strong CYP3A inhibitor must be used short-term (such as anti-infectives for seven days or less), interrupt ibrutinib for the duration of inhibitor use.
- If a strong CYP3A inhibitor must be used, the benefit outweighs the risk, and longer term dosing is required (for more than 7 days), reduce ibrutinib dose to 140 mg for the duration of inhibitor use.
 - If posaconazole at higher doses (suspension >200 mg twice daily), or IV or delayed-release formulations must be used, reduce ibrutinib dose to 140 mg for the duration of azole use
- If a moderate CYP3A inhibitor must be used, reduce ibrutinib to 280 mg for the duration of the inhibitor use.
 - If voriconazole, or doses ≤200 mg twice daily of posaconazole suspension are required, reduce ibrutinib dose to 140 mg for the duration of inhibitor use.
- No dose adjustment is required in combination with mild inhibitors.
- Subjects should be monitored closely for signs of ibrutinib toxicity
- After discontinuation of a CYP3A inhibitor, resume previous dose of ibrutinib

Avoid concomitant use of strong CYP3A inducers (eg, carbamazepine, rifampin, phenytoin, and St. John's Wort) as these medications/products could decrease ibrutinib concentrations. Consider alternative agents with less CYP3A induction.

In vitro studies indicated that ibrutinib is not a substrate of P-glycoprotein (P-gp).

A list of common CYP3A inhibitors and inducers is provided in [Appendix G](#). For further information, please refer to the current version of the [ibrutinib IB](#).

6.2.1.2. Concomitant Use with Venetoclax

- Concomitant use of venetoclax with strong CYP3A inhibitors at initiation and during ramp-up phase increases the risk for TLS. Concomitant use of venetoclax with strong CYP3A inhibitors at initiation and during ramp-up phase is contraindicated.
- For subjects who have completed the ramp-up phase and are on a steady daily dose of venetoclax, reduce the venetoclax dose by at least 75% when used concomitantly with a strong CYP3A inhibitor. See [Section 6.3.1](#) for prohibited CYP3A inhibitors.
- Avoid concomitant use of moderate CYP3A inhibitors with venetoclax. Consider alternative treatments. If a moderate CYP3A inhibitor must be used, reduce the doses of venetoclax by at least 50%. Monitor subjects more closely for signs of toxicities.
- Avoid concomitant use of strong CYP3A inhibitors with venetoclax. Consider alternative treatments. If a strong CYP3A inhibitor must be used, reduce the doses of venetoclax by at least 75%. Monitor subjects more closely for signs of toxicities.

Resume the venetoclax dose that was used prior to initiating the CYP3A inhibitor 2 to 3 days after discontinuation of the inhibitor.

A list of common CYP3A inhibitors, CYP3A inducers, and cautionary medications is provided in [Appendix G](#).

For preliminary venetoclax PK results with concurrent ibrutinib administration, see [Section 1.3.2.1](#). For further information, please refer to the current version of the [venetoclax IB](#).

Table 7. Management of Potential Ibrutinib and Venetoclax Interactions with CYP3A Inhibitors

Inhibitors	Venetoclax		Ibrutinib
	Initiation and Ramp-up Phase	Steady Daily Dose (After Ramp-up Phase)	At any time
Strong CYP3A Inhibitor	Contraindicated	Avoid inhibitor use, consider alternate. If must be used, reduce the venetoclax dose by at least 75%	Avoid inhibitor use, consider alternative agent. If must be used, withhold ibrutinib for duration of inhibitor use, or reduce ibrutinib to 140 mg
Moderate CYP3A Inhibitor	Avoid inhibitor use, consider alternative agent. If must be used, reduce the venetoclax dose by at least 50%		Avoid inhibitor use, consider alternative agent. If must be used, reduce ibrutinib to 280 mg

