b. Clinical TLS was defined as laboratory TLS with clinical consequences such as acute renal failure, cardiac arrhythmias, or sudden death and/or seizures.

Table 6. Dose Modification for Toxicity during Venetoclax Treatment

Dose at Interruption, mg	Restart Dose, mg ^a
400	300
300	200
200	100
100	50
50	20
20	10

- a. During the ramp-up phase, continue the reduced dose for 1 week before increasing the dose.

For required dose modification for concomitant treatment with CYP3A inhibitors refer to [Section 6.2.1.2](#).

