Appendix G. Sample List of Cautionary Medications

Cautionary medications are defined as follows. Refer to [Section 6.2.1.1](#) and [6.2.1.2](#) on instructions for concomitant use of CYP3A inhibitors and inducers with ibrutinib and venetoclax, respectively.

The below medications apply to both ibrutinib and venetoclax unless otherwise specified.

INHIBITORS OR INDUCERS		SUBSTRATES
Strong CYP3A inhibitors:	Strong CYP3A inducers:	Substrates of P-gp
boceprevir	Avasimibe	aliskiren
clarithromycin	Carbamazepine	ambrisentan
cobicistat	Phenobarbital	colchicines
conivaptan	Phenytoin	dabigatran etexilate
indinavir	Rifabutin	digoxin
itraconazole	Rifampin	everolimus
ketoconazole	St. John's Wort	fexofenadine
lopinavir		lapatinib
mibefradil		loperamide
nefazodone	Moderate CYP3A inducers:	maraviroc
nelfinavir	Bosentan	nilotinib
posaconazole	Efavirenz	ranolazine
ritonavir	Etravirine	saxagliptin
saquinavir	Modafinil	sirolimus
telaprevir	Nafcillin	sitagliptin
telithromycin	Oxcarbazepine	talinolol
troleandomycin	Troglitazone	tolvaptan
voriconazole*		topotecan
Moderate CYP3A inhibitors:	Weak CYP3A inducers:	Substrates of BCRP (Venetoclax only)
aprepitant	Amprenavir	methotrexate
amprenavir	aprepitant,	mitoxantrone
atazanavir	Armodafinil	irinotecan
ciprofloxacin	Clobazamechinacea	lapatinib
crizotinib	glucocorticoids (eg, prednisone)	rosuvastatin
darunavir	Nevirapine	sulfasalazine
dronedarone	Pioglitazone	topotecan
erythromycin	Rufinamide	
diltiazem	Vemurafenib	
fluconazole		
fosamprenavir		
imatinib		
isavuconazole		
verapamil		

INHIBITORS OR INDUCERS		SUBSTRATES
Weak CYP3A inhibitors:	Inhibitors of OATP1B1/B3 (Venetoclax)	Substrates of OATP1B1/B3 (Venetoclax only)
alprazolam	gemfibrozil,	atrasentan
amiodarone	Eltrombopag	atorvastatin
amlodipine	Cyclosporine	ezetimibe
atorvastatin	Tipranavir	fluvastatin
bicalutamide		glyburide
cilostazol		olmesartan
cimetidine	Inhibitors of BCRP (Venetoclax)	rosuvastatin
cyclosporine	Cyclosporine	simvastatin acid
fluvoxamine	Geftinib	pitavastatin
fluoxetine		pravastatin
ginkgo		repaglinide
goldenseal	Inhibitors of P-gp (Venetoclax)	telmisartan
isoniazid	Amiodarone	valsartan
nilotinib	Azithromycin	
oral contraceptives	Captopril	
pazopanib	Carvedilol	
ranitidine	Cyclosporine	
ranolazine	Dronedarone	
suboxone	Felodipine	
tipranavir/ritonavir	Quercetin	
ticagrelor	Quinidine	
zileuton	Ranolazine	
	Ticagrelor	

* moderate CYP3A inhibitor per ibrutinib human data / clinical studies

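### For voriconazole, the Appendix G footnote read with Table 7 gives ibrutinib 280 mg, while Protocol Section 6.2.1.1 requires 140 mg

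*Protocol*

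**What the plan says.** Four places in the Protocol bear on the ibrutinib dose when a subject needs voriconazole.

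- **Section 6.2** points to Appendix G for the sample list of drugs and to Table 7 "below for management of potential ibrutinib and venetoclax interactions with CYP3A inhibitors".
- **Section 6.2.1.1** gives the general rule: "If a moderate CYP3A inhibitor must be used, reduce ibrutinib to 280 mg for the duration of the inhibitor use". Directly beneath it, as a sub-bullet, is an exception: "If voriconazole, or doses ≤200 mg twice daily of posaconazole suspension are required, reduce ibrutinib dose to 140 mg".
- **Section 6.2.1.2, Table 7**, has one row for strong and one for moderate inhibitors and names no drug. The ibrutinib cell of the moderate row reads "Avoid inhibitor use, consider alternative agent. If must be used, reduce ibrutinib to 280 mg", with no exception and no pointer to Section 6.2.1.1. The ibrutinib cell of the strong row gives a choice between withholding ibrutinib and 140 mg.
- **Appendix G** lists voriconazole in the strong-inhibitor column with an asterisk, and the footnote reads "moderate CYP3A inhibitor per ibrutinib human data / clinical studies". The appendix opens by referring to Sections 6.2.1.1 and 6.2.1.2 "on instructions for concomitant use of CYP3A inhibitors and inducers with ibrutinib and venetoclax, respectively", and adds: "The below medications apply to both ibrutinib and venetoclax unless otherwise specified".

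The dose-modification sections also carry cross-references. The ibrutinib section (5.4.1.4) points to 6.2.1.1. The venetoclax section (5.4.2.5) ends with "For required dose modification for concomitant treatment with CYP3A inhibitors refer to" Section 6.2.1.2, where Table 7 sits and the voriconazole exception does not appear.

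**The concern.** Section 6.2 tells sites to look the drug up in Appendix G and manage it from Table 7. For voriconazole, a careful reader dosing ibrutinib would give the footnote weight over the column heading, because the footnote is the entry specific to ibrutinib. That reader arrives at the moderate row and 280 mg. Section 6.2.1.1 also places voriconazole under the moderate rule, so the moderate row is the matching row; the table has simply lost the exception that belongs to it.

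The error runs towards too much ibrutinib while its metabolism is inhibited. Sections 1.2.4.1 and 1.2.4.2 describe arrhythmic and hemorrhagic events with ibrutinib, some of them fatal. The situation is foreseeable. Section 1.2.4.5 reports fungal infections in treated subjects and advises considering prophylaxis in those at increased risk of opportunistic infection, Section 6.2.1.1 itself plans for voriconazole and posaconazole, and Section 7.1.4.1 provides PK sampling for subjects who have to start a moderate or strong inhibitor on treatment, although it does not name voriconazole.

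**Working it through.** This is a comparison of texts, not a statistical calculation. The only arithmetic is in capsules.

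**Inputs**
- Full ibrutinib dose: 420 mg/day as three 140 mg capsules (Section 5.4.1.2).
- Voriconazole dose in Section 6.2.1.1: 140 mg.
- Table 7, ibrutinib column: moderate row 280 mg; strong row withhold or 140 mg.
- Appendix G: voriconazole in the strong column, footnoted as moderate for ibrutinib.

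**Dose reached by each reading route**

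| Route | Class used | Ibrutinib per day | Share of 420 mg |
|---|---|---|---|
| Section 6.2.1.1 directly | moderate, with named exception | 140 mg (1 capsule) | 140/420 = 33% |
| Appendix G column, then Table 7 | strong | 0 or 140 mg (0 or 1 capsule) | 0% or 33% |
| Appendix G footnote, then Table 7 | moderate | 280 mg (2 capsules) | 280/420 = 67% |

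Only the third route exceeds the dose in Section 6.2.1.1. The excess is 280 − 140 = 140 mg/day, one capsule, and the ratio is 280/140 = 2.

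**Posaconazole.** Low-dose posaconazole suspension shares the same sub-bullet, but Appendix G lists posaconazole as strong with no footnote. The lookup therefore leads to the strong row (withhold or 140 mg), and the conflict does not arise. The point is specific to voriconazole.

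**Scope of the footnote.** Appendix G applies its lists to both drugs unless otherwise specified. If a reader extended the moderate label to venetoclax, Table 7 would change the instruction during initiation and ramp-up from contraindicated to a reduction of at least 50%. At the steady dose it would change a reduction of at least 75% to one of at least 50%. At 400 mg, the ceiling would move from 400 × 0.25 = 100 mg to 400 × 0.50 = 200 mg. The footnote's reference to ibrutinib data argues against that reading, but nothing states that voriconazole stays strong for venetoclax.

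**The case against.** The strongest reply is that no sentence in the Protocol prescribes 280 mg with voriconazole. The only instruction that names the drug gives 140 mg, and a named exception beside a general rule should govern over a class-level summary. Appendix G opens by sending ibrutinib readers to Section 6.2.1.1, and so does the ibrutinib dose-modification section. The venetoclax pointer to Section 6.2.1.2 naturally concerns venetoclax dosing, so it is weak evidence that sites are led away from the ibrutinib rule. A reader who follows the strong column is safe. Exposure is also narrow: subjects who require a strong inhibitor are excluded at entry (Section 4.2) and at reintroduction (Section 8.4), Section 5.4.1.2 says strong inhibitors should be avoided throughout, and Section 6.2.1.1 says to avoid both strong and moderate inhibitors with ibrutinib and to monitor closely for toxicity.

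All of that stands as a limit on the weight of the point. It shows that the right dose can be found and that few subjects should meet the situation. It does not make Table 7 correct. Section 6.2 designates the table for management, and nothing in it tells the reader that an exception exists. On the footnote's own classification, voriconazole is not a strong inhibitor for ibrutinib, so the exclusion of subjects needing strong inhibitors gives less protection on exactly this route.

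**Conclusion.** The inconsistency is real and limited to voriconazole. One of three available reading routes gives twice the ibrutinib dose that Section 6.2.1.1 requires, an excess of one 140 mg capsule a day for as long as the inhibitor is taken. This rests on two assumptions: that Section 6.2.1.1 is the governing instruction, because it alone names the drug, and that a reader gives the footnote precedence over the column heading without also consulting Section 6.2.1.1.

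The documents give neither the number of subjects who would receive voriconazole nor ibrutinib exposure in its presence. The factor of 2 is therefore a ratio of prescribed doses, not a measured risk. The 1-year disease-free survival comparison in the MRD cohort and the complete response rate in the Fixed Duration cohort are unaffected. It is a dosing-safety consistency point that should be corrected. The correction remains useful because ibrutinib can be reintroduced in both cohorts and Fixed Duration subjects are followed for about 10 years.

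**What to change.** Make two edits.

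1. In the ibrutinib cell of Table 7's moderate row, add that the dose is 140 mg if the inhibitor is voriconazole, with a reference to Section 6.2.1.1.
2. Reword the Appendix G footnote to say that the moderate classification applies to ibrutinib only, that ibrutinib is reduced to 140 mg per Section 6.2.1.1, and that voriconazole remains a strong inhibitor for venetoclax.

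The cost is one phrase in a table cell and one footnote, or a clarification letter to sites. No new assessments are needed, and no analysis changes.

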6.2.2. Drugs That May Have Their Plasma Concentrations Altered by Ibrutinib

In vitro studies indicated that ibrutinib is not a substrate of P-glycoprotein (P-gp), but is a mild inhibitor. Ibrutinib is not expected to have systemic drug-drug interactions with P-gp substrates.

However, it cannot be excluded that ibrutinib could inhibit intestinal P-gp after a therapeutic dose. There is no clinical data available. Therefore, to avoid a potential interaction in the GI tract, narrow therapeutic range P-gp substrates such as digoxin, should be taken at least 6 hours before or after ibrutinib.

6.2.3. Drugs That May Have Their Plasma Concentrations Altered by Venetoclax

Venetoclax is a P-gp and BCRP substrate as well as a P-gp and BCRP inhibitor and weak OATP1B1 inhibitor *in vitro*. To avoid a potential interaction in the gastrointestinal tract, co-administration of narrow therapeutic index P-gp substrates such as digoxin with venetoclax should be avoided. If a narrow therapeutic index P-gp substrate must be used, it should be taken at least 6 hours before venetoclax.

6.2.4. Antiplatelet Agents and Anticoagulants

Warfarin or vitamin K antagonists should not be administered concomitantly with ibrutinib. Supplements such as fish oil and vitamin E preparations should be avoided. In an *in vitro* platelet function study, inhibitory effects of ibrutinib on collagen-induced platelet aggregation were observed. Use of ibrutinib in subjects requiring other anticoagulants or medications that inhibit platelet function may increase the risk of bleeding. Subjects with congenital bleeding diathesis have not been studied. For guidance on ibrutinib and the use of anticoagulants during procedures/surgeries see [Section 6.4](#).

Subjects requiring the initiation of therapeutic anticoagulation therapy (eg, atrial fibrillation), consider the risks and benefits of continuing ibrutinib treatment. If therapeutic anticoagulation is clinically indicated, treatment with ibrutinib should be held and not be restarted until the subject is clinically stable and has no signs of bleeding. Subjects should be observed closely for signs and symptoms of bleeding. No dose reduction is required when study drug is restarted.

In a drug-drug interaction study in healthy subjects, administration of a single dose of venetoclax with warfarin resulted in an 18% to 28% increase in C_{max} and AUC_{∞} of R-warfarin and S-warfarin. Because venetoclax was not dosed to steady state, it is recommended that the international normalized ratio (INR) be monitored closely in subjects receiving warfarin.

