5.4.1.2. Dose and Administration

Ibrutinib 420 mg (3 x 140-mg capsules) is administered orally once daily. The capsules are to be taken around the same time each day with 8 ounces (approximately 240 mL) of water. The capsules should be swallowed intact and subjects should not attempt to open capsules or dissolve them in water. During cycles with venetoclax combination dosing, ibrutinib and venetoclax

should be taken together at the same time, with 8 ounces of water and with a meal (or within 30 minutes after the completion of a meal). For subjects not able to swallow all ibrutinib capsules and venetoclax tablets at the same time, administration should be completed within a 60-minute window. The use of strong CYP3A inhibitors/inducers, and grapefruit, Seville oranges, and starfruit should be avoided for the duration of the study ([Appendix G](#)).

If a dose is not taken at the scheduled time, it can be taken as soon as possible on the same day with a return to the normal schedule the following day. The subject should not take extra capsules to make up the missed dose.

The first dose will be delivered in the clinic on Day 1, after which subsequent dosing is typically on an outpatient basis. On days of PK sample collection (C2D1 and C6D1), ibrutinib and venetoclax should be administered at the same time or as close together in time as possible in the clinic. Ibrutinib will be dispensed to subjects in bottles at each visit. Unused ibrutinib dispensed during previous visits must be returned to the site and drug accountability records ([Section 12.8](#)) updated at each visit. Returned capsules must not be redispensed to anyone.

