5.4.1.4. Dose Modification for Adverse Reactions

The dose of study drug must be modified according to the dose modification guidance in [Table 2](#) and [Table 3](#) if any of the following toxicities occur:

- Grade 3 or greater neutropenia with infection or fever
- Grade 4 neutropenia (ANC <500/ μ L) for more than 7 days. See [Section 6.1](#) for instructions regarding the use of growth factor support.
- Grade 3 thrombocytopenia (platelets <50,000/ μ L) in the presence of clinically significant bleeding events.
- Grade 4 thrombocytopenia (platelets <25,000/ μ L).

- Grade 3 or greater non-hematological toxicity (Note: [Table 3](#) includes recommendations for cardiac failure and cardiac arrhythmias)
- Grade 2 cardiac failure ([Table 3](#))
- Any other Grade 4 or unmanageable Grade 3 hematological toxicity.

If clinically indicated, the use of anticoagulants or antiplatelet agents may be considered for the thromboprophylaxis of atrial fibrillation ([Section 6.2.4](#)).

In the event that the investigator feels deviation from the recommendations above is required, please consult the Medical Monitor.

Dose changes must be recorded in the Dose Administration eCRF. Study treatment should be discontinued in the event of an ibrutinib-related toxicity requiring dose hold lasting more than 28 days, unless reviewed and acknowledged by the Medical Monitor.

Note: Temporary withholding of single-agent ibrutinib for as little as 7 days can cause a transient worsening of disease and/or of constitutional symptoms. Study drug should be re-started as soon as clinically appropriate.

Table 2. Ibrutinib/ Placebo Dose Modifications for Events not Specified in Table 3

Occurrence	Action to be Taken
First	Withhold study drug until recovery to Grade ≤ 1 or baseline; may restart at original dose level ^a
Second	Withhold study drug until recovery to Grade ≤ 1 or baseline; may restart at 1 dose level lower (ie, 280 mg/day for 420 mg/day dose)
Third	Withhold study drug until recovery to Grade ≤ 1 or baseline; may restart at 1 dose level lower (ie, 140 mg/day for 420 mg/day dose)
Fourth	Discontinue study drug

a. When resuming treatment, restart at the same or lower dose based on benefit-risk evaluation. If the toxicity reoccurs, reduce daily dose by 140 mg.

For required dose modification for hepatic impairment refer to [Section 5.4.1.6](#) and for concomitant treatment with CYP3A inhibitors refer to [Section 6.2.1.1](#).

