Table 3. Ibrutinib/Placebo Dose Modifications for Cardiac Failure or Cardiac Arrhythmias

Events	Occurrence	Action
Grade 2 cardiac failure	First	Hold study drug until recovery to Grade ≤ 1 or baseline; restart at 1 dose level lower (2 capsules [ie, 280 mg daily])
	Second	Hold study drug until recovery to Grade ≤ 1 or baseline; restart at 1 dose level lower (1 capsules [ie, 140 mg daily])
	Third	Discontinue study drug
Grade 3 cardiac arrhythmias	First	Hold study drug until recovery to Grade ≤ 1 or baseline; restart at 1 dose level lower (2 capsules [ie, 280 mg daily]) ^a
	Second	Discontinue study drug
Grade 3 or 4 cardiac failure Grade 4 cardiac arrhythmias	First	Discontinue study drug

a. Evaluate the benefit-risk before resuming treatment.

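### Protocol section 6.2.4 and Table 3 give different restart conditions and doses for a first Grade 3 atrial fibrillation that leads to anticoagulation, and nothing says which governs

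*Protocol*

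**What the plan says.** The full dose is set in protocol section 5.4.1.2: "Ibrutinib 420 mg (3 x 140-mg capsules) is administered orally once daily".

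Section 5.4.1.4 is binding in tone. It states "The dose of study drug must be modified according to the dose modification guidance in" Tables 2 and 3 if any of a list of toxicities occurs. The list includes non-hematological toxicity of Grade 3 or greater, with a note that Table 3 deals with cardiac failure and arrhythmias. For a first Grade 3 cardiac arrhythmia, Table 3 says to hold until recovery to Grade 1 or lower or baseline, then "restart at 1 dose level lower (2 capsules [ie, 280 mg daily". Its footnote adds "Evaluate the benefit-risk before resuming treatment". A second Grade 3 arrhythmia, or any Grade 4 arrhythmia, means stopping the drug.

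Below its list of toxicities, section 5.4.1.4 also says that, where clinically indicated, "the use of anticoagulants or antiplatelet agents may be considered for the thromboprophylaxis of atrial fibrillation", and cites section 6.2.4.

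Section 6.2.4 begins its instruction with "Subjects requiring the initiation of therapeutic anticoagulation therapy (eg, atrial fibrillation), consider the risks and benefits of continuing ibrutinib treatment". If anticoagulation is indicated, "treatment with ibrutinib should be held and not be restarted until the subject is clinically stable and has no signs of bleeding". It then says "No dose reduction is required when study drug is restarted". It sets no grade limit on the atrial fibrillation example and does not mention Table 3.

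**The concern.** Atrial fibrillation is the one condition that section 6.2.4 names, and it is also a cardiac arrhythmia under Table 3. When the event is Grade 3 and leads to therapeutic anticoagulation, one section says a reduction must be made and the other says none is required. They also set different conditions for restarting.

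Two sites could each follow a section of the protocol and treat the same event differently. This is a safety matter, because section 1.2.4.1 lists atrial fibrillation among the cardiac risks of ibrutinib. Ibrutinib is given in both cohorts, and Table 3 is written for ibrutinib/placebo, so the question also arises in the double-blind phase. SAP section 3.4 summarizes relative dose intensity and dose reductions due to adverse events, and SAP Table 3 lists treatment-emergent events leading to dose reduction. Those summaries would partly reflect which section a site happened to read.

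**Working it through.** The plan gives no figure to reproduce, so the check is a comparison of text. The case is a subject on 420 mg daily with a first Grade 3 atrial fibrillation who starts therapeutic anticoagulation.

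| | Section 6.2.4 | Section 5.4.1.4 with Table 3 |
|---|---|---|
| Trigger | Start of therapeutic anticoagulation; atrial fibrillation is the example; any grade | Grade 3 cardiac arrhythmia, first occurrence |
| Action | Hold | Hold |
| Condition for restart | Clinical stability and no bleeding | Grade 1 or lower, or baseline |
| Dose at restart | No reduction required | One level lower, 280 mg |
| Force | Statement that a reduction is not needed | Modification is mandatory |
| Second Grade 3 event | Not addressed | Discontinue |

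1. **Do both rules reach this subject?** Yes. The event meets the Grade 3 entry in section 5.4.1.4 and the arrhythmia row of Table 3. The start of anticoagulation for atrial fibrillation meets section 6.2.4. Neither section excludes the other's cases.

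2. **How far apart are the doses?** If the subject returns to the previous dose under section 6.2.4, that is 420 mg; under Table 3 it is 280 mg. The difference is 420 − 280 = 140 mg, one capsule, and 140/420 = one third of the dose.

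3. **Do the restart conditions coincide?** No. Stability without bleeding does not necessarily mean recovery to Grade 1 or lower or baseline, nor the reverse.

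4. **Does any other text settle it?**
   - Section 1.2.4.1 refers persisting arrhythmias to section 5.4.1.4, with nothing on anticoagulated subjects.
   - Section 1.2.4.2 refers questions on anticoagulants to section 6.2.4.
   - The footnote to Table 3 asks for a benefit-risk evaluation and says nothing about anticoagulation.
   - None of these ranks the two rules.

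5. **Where does the overlap end?** Table 3 has no row for Grade 1 or 2 arrhythmia, so the two restart rules do not clash there. For a second Grade 3 event or a Grade 4 event, Table 3 says discontinue, and section 6.2.4 gives no recurrence rule or grade-specific instruction to set against it.

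**The case against.** The best defense is that the two rules have different triggers and can both be obeyed. Section 6.2.4 sits in the chapter on concomitant medication, so its last sentence may mean only that anticoagulation by itself does not call for a lower dose. The arrhythmia would then still be handled by Table 3. A site that waits for both restart conditions and then applies Table 3 breaches neither section. Section 1.2.4.1 points persisting arrhythmias to section 5.4.1.4, and section 5.4.1.4 tells an investigator who wants to depart from its guidance to consult the Medical Monitor.

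Much of this stands as a plausible account of intent. Section 6.2.4 does not order a restart at 420 mg; it says a reduction is not required. But the limiting words are absent. The sentence is unqualified and belongs to an instruction whose only example is atrial fibrillation. A site relying on it could restart at 420 mg and so breach section 5.4.1.4. That site would have no reason to think it was deviating, so the Medical Monitor route might never be used.

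Three stronger readings are tempting and are not supported:

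- **That the sections conflict over a second Grade 3 event.** Section 6.2.4 is silent on recurrence and nowhere directs a restart after one. Silence does not contradict Table 3's instruction to discontinue.
- **That section 5.4.1.4 hands the dosing of atrial fibrillation to section 6.2.4.** It cites that section only for the use of anticoagulants or antiplatelet agents.
- **That at least about 8 subjects would be affected.** A reader could take the 3% listing threshold for Grade 3 or 4 atrial fibrillation in section 1.2.3.1 and compute 0.03 × (150 + 125) = 8.25. That threshold comes from pooled monotherapy data (N=1318) and combines Grades 3 and 4. Section 1.2.3.2, on combination studies (N=423, with partner drugs other than venetoclax), does not list atrial fibrillation among Grade 3 or 4 events at 3% or more. The trial also excludes uncontrolled arrhythmia and caps age at 70. The share of cases needing anticoagulation is not given. The figure is neither a floor nor an estimate.

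**Conclusion.** The protocol is wrong as written: it is internally inconsistent on one defined case. For a first Grade 3 atrial fibrillation in a subject on 420 mg who also starts therapeutic anticoagulation, it gives two restart conditions and two positions on dose, 140 mg apart, with no order of precedence. This conclusion rests only on the wording of sections 6.2.4 and 5.4.1.4 and Table 3, and on atrial fibrillation counting as a cardiac arrhythmia, which section 1.2.4.1 supports by its title and content.

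The scope is narrow. How many subjects meet all the conditions cannot be derived from the documents. No endpoint definition or hypothesis test turns on the point; the statistical effect is confined to descriptive exposure and adverse-event summaries. The reason to correct it is subject safety and uniform conduct across sites. Nothing here implies that either dose or either restart condition is the right one.

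**What to change.** Reconcile section 6.2.4 with section 5.4.1.4 and Table 3:

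- State which passage governs the restart condition and the restart dose when a Table 3 arrhythmia is also the reason for anticoagulation.
- Limit the dose sentence in section 6.2.4 to the situations it is meant for.
- Add a cross-reference from section 6.2.4 to Table 3.

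Which rule applies is for the sponsor's clinical team to decide. The cost is about one clarifying sentence and a cross-reference, in the next amendment or a letter to sites. It needs no change to the sample size, the hypotheses or the planned analyses.
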